Title: Non-invasive versus invasive blood pressure measurement in the morbidly obese parturient (BMI \geq 40 kg/m²) with severe preeclampsia: A comparison of direct arterial blood pressure measurements with readings obtained using either large cylindrical, radial cylindrical, or novel conical bariatric upper arm blood pressure cuffs.

Co-Investigators: [name]; [name] Sub-Investigators: [name]; [name]

; [name]; [name], [name], [name], MD, [name]

Vanderbilt University Medical Center

OB Anesthesiology

Aim: To compare agreement of invasive blood pressure measurements with non-invasive blood pressure measurements measured with a conical blood pressure, radial cuff, and large standard upper arm rectangular cuff in morbidly obese severely hypertensive (systolic blood pressure > 160 mmHg) parturients.

Background and Significance: A morbidly obese [Body Mass Index (BMI) \geq 40 kg/m²] pregnant woman is at singular risk for all the complications of pregnancy, most notably preeclampsia (PE) ^{1, 2}. Furthermore a woman who is already chronically hypertensive is quite likely to develop superimposed PE ^{3,4}. Uncontrolled systolic hypertension in pregnancy prompts placental abruption, hemorrhagic stroke, and systolic or diastolic heart failure. Mhyre rightly asserts that: "Systolic blood pressure ... above 160 mm Hg constitutes a hypertensive crisis in a pregnant woman and requires urgent treatment to minimize risk for cerebral hemorrhage" ⁵. The American College of Obstetrics and Gynecology Task Force on Hypertension in Pregnancy also now recommends the use of antihypertensive therapy for persistent severe maternal hypertension (SBP at or above 160 mm Hg) ⁶. Accurate blood pressure measurement is therefore a prerequisite to controlling dangerously high SBP to enable labor and delivery to be conducted safely in association with PE. An algorithm has been implanted on Vanderbilt Labor and Delivery, using SMFM guidelines, to guide treatment of these severe range blood pressures²⁰. Precise SBP measurement is also a precondition for clinically testing hypotheses concerning the existence of druggable targets that will allow prolongation of pregnancy in the face of severe PE and /or intra-uterine growth restriction (IUGR) remote from term ^{7,8}.

Hypertensive hemorrhagic stroke is the most common cause of maternal death related to preeclampsia 5 . Upper arm SBPs measured with a standard rectangular cylindrical cuff exceeding 160 mm Hg are not infrequently seen in severe preeclampsia. During general anesthesia for cesarean section direct arterial SBPs well in excess of 160 mm Hg have been recorded during both laryngeal intubation and extubation 9,10 . SBPs this high place the preeclamptic parturient at serious risk for hemorrhagic stroke 5 . We hypothesize that measurement of noninvasive blood pressure (NIBP) in morbidly obese patients (BMI \geq 40) with large upper arm circumferences

adds a further margin of under-reading error when compared with direct arterial, invasive blood pressure (IBP) recording, thus compounding the risk of maternal stroke.

Oscillometric NIBP measurement is the customary standard blood pressure monitoring method most often used in the labor suite and obstetric operating room today. For this purpose a rectangular, cylindrical blood pressure (BP) cuff placed on the upper arm is connected to an oscillometric blood pressure device. Yet inaccuracies related to the fact that oscillometric NIBP devices under-read high SBP relative to IBP measurements have been recognized as a potential source of maternal morbidity for years ¹¹. A decade ago Martin et al. highlighted the importance of treating SBP rather than diastolic blood pressure (DAP) to avoid stroke in severe preeclampsia and eclampsia, concluding that: "A paradigm shift is needed toward considering antihypertensive therapy for severely preeclamptic and eclamptic patients when systolic blood pressure reaches or exceeds 150-160 mm Hg." ¹².

In non-pregnant patients a recent retrospective analysis of data obtained from a cohort of more than 15,000 men and women showed that systolic, mean, and diastolic upper arm blood pressures measured non-invasively with rectangular, cylindrical blood pressure cuffs that fell within the normal range correlated relatively well with direct IBP recordings obtained via a radial artery catheter, the latter method currently representing the "gold standard" for clinical BP determination ¹³. However, outside the normal ranges NIBP tended to under read at higher pressures but paradoxically, over read at lower blood pressures. Cross over points for SBP, MAP and DAP agreement between NIBP and IBP were noted to be 111, 95 and 80 mm Hg respectively. Similar disparities between NIBP and IBP recordings in hyperacute stroke patients have been documented ¹⁴. A recent systematic review of the subject under scrutiny here confirms the relative inaccuracy of current NIBP methods when compared to IBP recording ¹⁵.

Rectangular, cylindrical BP cuffs have been noted to overestimate SBP relative to tronchoconical cuffs in morbidly obese (mean body mass index $41.4 \pm \text{SEM } 0.7$) men and women (group 4) by as much as 9.7 mm Hg , most notably in those subjects with shorter upper arm lengths 16 . The incidence of hypertension among this group of morbidly obese patients was purported to be 54.6% using the cylindrical cuff, but was found to be only 40.0% using the conical cuff (p < 0.001). Thus 15% of subjects who appeared hypertensive with the cylindrical cuff were actually normotensive. In contrast, in a limited study of "severely" obese male and female subjects (n = 16) NIBPs measured on the upper arm with both cylindrical and conical cuffs, and on the forearm with cylindrical cuffs were noted to be little different from corresponding radial artery catheter pressures 17 .

With regard to pregnancy, Langenegger et al. compared both manual ausculatory and automated oscillometric NIBP to direct arterial IBP when monitoring acute severe hypertension in 23 preeclamptic patients (gestational ages 22 - 40 weeks; BMI 19 - 45) 18 . Mean oscillometric SBP (148 \pm 18 mm Hg) and manual auscultatory readings (152 \pm 15) were on average 24 \pm 17 and 20 \pm 15 mm Hg respectively lower than the direct arterial SBP recordings (172 \pm 11 mm Hg). To

the best of our knowledge, no such comparisons have yet been made in a cohort of morbidly obese (BMI \geq 40) pregnant women manifesting severe hypertension.

The conical Ultracheck Curve (reusable or single use) BP cuff (Statcorp Medical, Jacksonville, Florida, U.S.A.) is advertised (Sharn Anesthesia Inc., Tampa, Florida, U.S.A.) as: "A Breakthrough Solution for Accurate Bariatric Blood Pressure Readings. We intend to compare IBP readings obtained from morbidly obese, severely hypertensive (SBP > 160 mm Hg) parturients with NIBP consecutively measured with new innovative conical Ultracheck Curve BP cuffs and large standard upper arm rectangular cylindrical as well as radial BP cuffs.

Methods: Twenty-five morbidly obese (BMI \geq 40 kg/m²) severely hypertensive (SBP > 160 mm Hg) parturients with clinically indicated radial artery lines already in situ or who agree to placement of an arterial line after a thorough explanation of limited complications related to arterial line insertion will be recruited to the study. Both IRB approval and the patients' written informed consent for the study will be obtained. The following measurements (left and right arm) will be made and recorded with the patient lying in a 15° left lateral tilt position, arms by their side and forearms pronated:

- 1) Proximal upper arm circumference just below the axilla.
- 2) Distal upper arm circumference 0.5 cm above antecubital fossa.
- 3) Upper arm length axilla to the antecubital fossa.
- 4) Blood pressure cuff size

For comparative purposes BP will be measured and documented sequentially and in random order (computer generated random numbers table). NIBPs will be recorded using either an upper arm large adult [American Heart Association (AHA): 16-36 cm.] cylindrical BP cuff, a radial cuff, or an UltraCheck Curve bariatric BP cuff. The BP cuffs will be linked to an Oscillometric BP recording device (Philips M1574A). There will be an initial set of readings on admission, and subsequent sets of readings before a medication administration on the Vanderbilt Management Guideline for Acute Hypertension Algorithm. A set of readings will also be attained at decision for ICU transfer or cesarean section. SBP, MAP and DAP will be recorded from each cuff site (3 cuffs total) and then repeated after swapping the cuffs over to the opposite arm . Direct invasive arterial pressure readings will be charted simultaneously for comparative purposes.

The primary outcome of this investigation will be to compare the agreement of NIBP and SBP measurements relative to IBP SBP recordings. Secondary outcomes will be: To compare the agreement of MAP and DAP NIBP recordings with IBP levels; to compare agreement of the SBP, MAP and DAP NIBP measurements obtained with cylindrical upper arm and radial BP cuffs with those recorded using conical BP cuffs.

Agreement between devices (NIBP vs IBP and NIBP cylindrical (upper and radial) versus conical BP cuffs) will be determined. The relationship between upper arm circumference minus distal arm circumference and upper arm cylindrical pressure and intra-arterial SBP difference

will be defined as well. The same relationship between upper arm minus distal arm circumference and conical cuff and intra-arterial SBP recordings differences will also be assessed.

Main Inclusion Criteria:

Written, signed and dated informed consent

 \geq 18 years of age

Morbidly obese (BMI \geq 40 kg/m²) severely hypertensive (SBP > 160 mm Hg) parturients with clinically indicated radial artery lines already in situ or who agree to placement of an arterial line after a thorough explanation of limited complications related to arterial line insertion will be recruited to the study

Gestational age greater than or equal to 24 weeks Parturients admitted for induction of labor

Exclusion Criteria:

Parturients admitted in labor

Statistical Plan:

Bland-Altman plots will be used to look at agreement of NIBP (SBP, MAP and DAP) and IBP. Regression analyses will examine the relationship between upper and lower forearm circumference measurements and difference between NIBP (SBP, MAP and DAP) cylindrical and radial cuffs versus conical (obesity) BP cuffs.

Based on the 2012 report from South Africa¹⁷ we estimate that 25 patients will initially need to be investigated. A difference of 10 mm Hg (SBP, MAP and DAP) will be considered clinically significant.

References:

- 3. Bramham K1, Parnell B, Nelson-Piercy C, Seed PT, Poston L, Chappell LC. Chronic hypertension and pregnancy outcomes: systematic review and meta-analysis BMJ. 2014 Apr 15;348:g2301. doi: 10.1136/bmj.g2301.

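### Cuff order is random but no balancing is described, the starting arm and second-arm order are not stated, and no order, pass or arm term is planned: a small, avoidable source of noise

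*Combined protocol and SAP*

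**What the plan says.** The ordering rule is one sentence in Methods: "BP will be measured and documented sequentially and in random order (computer generated random numbers table". Readings from the three cuffs are "then repeated after swapping the cuffs over to the opposite arm". For the reference, "Direct invasive arterial pressure readings will be charted simultaneously for comparative purposes". Sets recur: "There will be an initial set of readings on admission, and subsequent sets of readings before a medication administration", with a further set at the decision for ICU transfer or cesarean section.

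Methods does not say whether the order is drawn per woman, per set or per arm. It does not say whether the list is restricted in any way, which arm comes first, or what order applies on the second arm.

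The primary outcome is agreement of cuff systolic pressure with intra-arterial systolic pressure. Agreement of the cylindrical and radial cuffs with the conical cuff is secondary. The Statistical Plan names Bland-Altman plots and regressions on arm circumference. It includes no term for order, pass or arm. It states that "A difference of 10 mm Hg (SBP, MAP and DAP) will be considered clinically significant".

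**The concern.** Three cuffs are inflated in turn, then again on the other arm. A later reading may differ from an earlier one for two reasons: the woman's pressure has moved, or earlier inflations have changed the arm locally. If one cuff happens to come early more often than another, part of that difference is read as a difference between cuffs.

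A list that is random but unbalanced leaves this to chance, and 25 women is too few for chance to even it out reliably. Nothing stated makes the second pass offset the first, so a cuff drawn first could be first on both arms. With no order term planned, the analysis would not recover what the design leaves uneven.

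The outcome most at stake is the cuff-versus-cuff comparison, because the plan does not say that intra-arterial pressure is subtracted there.

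**Working it through.** **Inputs.** From the documents: 25 women, 3 cuffs, 2 arms and the 10 mm Hg threshold (Methods, Statistical Plan), and an SD of 17 mm Hg for oscillometric minus intra-arterial systolic pressure in the cited pregnancy study (Background and Significance). Assumptions: one unrestricted order per woman, and a linear position effect of 1 to 3 mm Hg per step. The documents report no position effect.

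**The plan's own figure.** With a difference of 10, SD 17, two-sided 5% and 80% power (the last two assumed), n = (17 × (1.960 + 0.842) / 10)² = 22.7, so 23. The exact t calculation gives 25, with power 80.6%. The planned 25 is therefore reproducible, though not from these inputs alone: SD 15 with 90% power gives 24 or 26. Nothing below changes the sample size.

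**Imbalance in counts.** There are 6 orders of 3 cuffs, so each cuff is first with probability 1/3. In 200,000 simulated trials of 25 unrestricted orders, the gap between the cuffs most and least often first has median 5:

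| Gap in times first | Share of trials |
|---|---|
| 4 or more | 67% |
| 5 or more | 50% |
| 6 or more | 38% |
| 8 or more | 15% |

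At least one of the six orders is never used in 6% of trials.

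**Translation to mm Hg.** Over the six orders, two cuffs differ in position by ±1 in four and by ±2 in two. The variance is (4 × 1 + 2 × 4)/6 = 2, so the SD is 1.41 positions per pass.

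| Second pass | SD of position gap, one woman | Same, at 1–3 mm Hg per step | SD of gap in 25-woman mean | Same, at 1–3 mm Hg per step |
|---|---|---|---|---|
| Same order reused | √2 = 1.41 | 1.4–4.2 mm Hg | √(2/25) = 0.28 | 0.3–0.8 mm Hg |
| Order redrawn | √(2/2) = 1.0 | 1.0–3.0 mm Hg | √(1/25) = 0.20 | 0.2–0.6 mm Hg |
| Order reversed | 0 | 0 | 0 | 0 |

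With the order reused, 95% of trials have a gap in mean position within 0.56 for a given pair of cuffs. At 3 mm Hg per step that is 0.56 × 3 = 1.7 mm Hg. If the order is redrawn for each set, the SD of 0.28 falls to √(2/50) = 0.20 over 50 sets and √(2/100) = 0.14 over 100.

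**Primary comparison.** One cuff's position has variance 2/3. At 3 mm Hg per step that is an SD of 3 × √(2/3) = 2.4 mm Hg. Added to 17 it gives √(17² + 2.4²) = 17.2, about 1% more. This treats the whole effect as local to the cuff, with nothing cancelling.

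**Balanced list without reversal.** Four complete sets of the 6 orders plus one woman put each cuff in each position 8 or 9 times. Mean positions are 1.96, 2.00 and 2.04, so the largest gap is 0.08.

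**Non-linear effect.** Suppose the first inflation on an arm differs from the later two by d (effects 0, d, d). Reversal gives the three cuffs means of d/2, d and d/2. The between-cuff SD for one woman is then √((4/6) × d²/4) = 0.41d, against 0.58d if redrawn and 0.82d if reused. Reversal reduces this effect but does not remove it. The six balanced orders even out the remainder across women.

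**Starting arm.** If one side always starts, side and pass coincide (25:0). A coin flip would give 9:16 or worse in 23% of trials. Balanced allocation gives 12:13.

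**The case against.** The plan already randomises the order, so there is no systematic order bias to remove. The 50% figure describes counts, not error in a result. In mm Hg the error in a between-cuff mean stays below 1 as an SD, on an effect size that the documents do not supply. Pressure trends, and a pressure rise from discomfort, are systemic. They appear in the simultaneous intra-arterial reading and largely cancel in the primary difference. All of this stands.

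A reader might infer stronger readings, which the documents do not support:

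- **That the list is simple random and the starting arm is not randomised.** Methods is silent on both. It describes no restriction but excludes none, and arm is tied to time across women only if one side always starts.
- **That arm confounds the comparison of cuffs.** Every cuff is used on both arms, and no left-right or first-second contrast is planned.
- **That reversing the order removes the problem entirely.** That holds only for a linear effect that is equal on both arms.

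Three things survive the objection. A purely local effect of earlier inflations is not visible in the intra-arterial reading. Drift enters cuff-versus-cuff comparisons wherever the reference is not subtracted. And extra spread within a woman widens Bland-Altman limits between cuffs and would look like device disagreement.

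**Conclusion.** The plan specifies no balanced cuff sequence, starting arm or second-arm order, and no analysis term that would make up for it. The consequence is added noise in the secondary cuff-versus-cuff comparisons. In a between-cuff mean it is an SD of about 0.3 to 0.8 mm Hg with the order reused on both arms, about 0.2 to 0.6 with it redrawn for the second arm, and less with a fresh draw for each set. All are small against 10 mm Hg. For a single woman's cuff difference the added SD is 1.0 to 4.2 mm Hg across the two cases.

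These figures rest on an unrestricted draw per woman and an assumed 1 to 3 mm Hg per step. The primary comparison is little affected. This is a free improvement with a modest gain, not a threat to the trial's conclusions.

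**What to change.** Before the start, replace the random list with a balanced one and state it in Methods:

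1. Cross the 6 cuff orders with the 2 starting arms to give 12 sequences, and permute them at random in blocks of 12 for the admission set. Twenty-four women fill two blocks and the 25th opens a third.
2. On the second arm, run the cuffs in reverse order (A-B-C, then C-B-A).
3. Draw later sets from a separate balanced list. Their number per woman is not fixed, so they should not disturb the balance of the admission set.

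The two parts do different work. Reversal removes a linear position effect within each woman and reduces a non-linear one. The balanced orders even out what is left across women.

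The cost is a new list and a sentence or two in Methods. It needs no extra women, readings or staff, and the sample size stays at 25.

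### The two upper-arm cuffs differ in size class as well as shape, and the taper analyses leave out absolute arm size, so cuff misfit could pass for a taper or shape effect

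*Combined protocol and SAP*

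**What the plan says.** The Methods name the cuffs as an "upper arm large adult [American Heart Association (AHA): 16-36 cm.] cylindrical BP cuff, a radial cuff, or an UltraCheck Curve bariatric BP cuff". The Background describes the comparison as "new innovative conical Ultracheck Curve BP cuffs and large standard upper arm rectangular cylindrical as well as radial BP cuffs", and the Statistical Plan contrasts "cylindrical and radial cuffs versus conical (obesity) BP cuffs".

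The Background hypothesis concerns women with BMI of at least 40 "with large upper arm circumferences". Eligibility sets no limit on arm size. The Background also reports that "Rectangular, cylindrical BP cuffs have been noted to overestimate SBP relative to tronchoconical cuffs in morbidly obese" adults, by up to 9.7 mm Hg. The Statistical Plan treats 10 mm Hg as clinically significant.

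For both arms the Methods record "Proximal upper arm circumference just below the axilla", a distal upper-arm circumference, upper-arm length, and "Blood pressure cuff size".

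Three planned analyses bear on the point:
- The secondary outcomes compare cylindrical and radial readings with conical readings.
- The text after the outcomes defines a taper analysis: "The relationship between upper arm circumference minus distal arm circumference and upper arm cylindrical pressure and intra-arterial SBP difference". It is repeated for the conical cuff.
- The Statistical Plan regresses cuff-versus-cuff differences on circumferences. It places these at the forearm, although the Methods measure the upper arm.

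The documents do not say what 16-36 cm describes, what arm range the conical or radial cuff covers, or how a size is chosen. No analysis uses the recorded cuff size.

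**The concern.** A cylindrical-versus-conical difference, or a taper slope seen only with the cylindrical cuff, invites the reading that the conical shape is better. Here the two upper-arm cuffs are a large adult size and a bariatric size, so they differ in size class too. A cuff too small for the arm can produce an error of its own. If that error grows with arm size, and larger arms also taper more, a regression on taper alone will credit taper with what belongs to size. At stake are the cuff-versus-cuff secondary outcome and the two taper analyses. The primary outcome is not affected.

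**Working it through.** The documents state no figure for cuff fit, so there is nothing of the plan's own to reproduce. What follows shows how large the problem could be. **Every arm size, correlation and misfit error below is an assumption.** Only 36 cm, 9.7 mm Hg, 10 mm Hg and the 25 women come from the documents.

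**Step 1. Share of arms beyond the cylindrical cuff.** Take mid-arm circumference as normal with mean m = 38 to 44 cm and SD s = 4 or 5 cm. The share above a limit L is 1 − Φ((L − m)/s).

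| Reading of 16-36 cm | L | Lowest share | Highest share |
|---|---|---|---|
| Arm range | 36 cm | m = 38, s = 5: 1 − Φ(−0.40) = 66% | m = 44, s = 4: 1 − Φ(−2.00) = 98% |
| Bladder length, 80% coverage assumed | 36/0.8 = 45 cm | m = 38, s = 4: 1 − Φ(1.75) = 4% | m = 44, s = 5: 1 − Φ(0.20) = 42% |

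The two readings together span 4% to 98%.

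**Step 2. Spurious cylindrical-minus-conical difference.** Suppose shape has no effect and a misfitting arm adds b mm Hg to the cylindrical reading. The mean difference is then share × b. For b = 5 to 15:
- at a 25% share, 0.25 × 5 = 1.3 to 0.25 × 15 = 3.8 mm Hg;
- at a 90% share, 0.90 × 5 = 4.5 to 0.90 × 15 = 13.5 mm Hg.

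Set against the 10 mm Hg criterion and the cited 9.7 mm Hg, this runs from minor to the whole effect.

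**Step 3. Spurious taper slope.** Let the cylindrical error be b × max(c − 36, 0), with c normal (mean m, SD 4 cm), taper SD 2 cm, correlation r between taper and c, and a true taper effect of zero. The expected slope on taper alone is b × P(c > 36) × r × 4/2.
- m = 38, b = 1, r = 0.5: 1 × 0.69 × 0.5 × 2 = 0.69 mm Hg per cm (simulated 0.71).
- m = 42, b = 1, r = 0.5: 1 × 0.93 × 0.5 × 2 = 0.93 (simulated 0.94).
- r = 0: zero.

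The simulation used 4,000 runs of 25 women, one value per woman, residual SD 8 mm Hg, m = 38 or 42 and b = 0.5 to 2 mm Hg per cm. The share of runs with a falsely significant taper slope (two-sided 5% level) was:

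| r | Taper alone | Taper plus circumference |
|---|---|---|
| 0 | about 5% | 4-6% |
| 0.3 | 6-16% | 4-5% |
| 0.5 | 7-39% | 4-5% |
| 0.7 | 8-69% | 5% |

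A larger residual SD would lower the middle column but leave the biased slope unchanged. If misfit made the cuff read low instead of high, the signs would reverse and the rates would not change.

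**Step 4. What adjustment does and does not do.** Adding circumference separates taper from arm size. It does not separate shape from size class in the mean cuff-versus-cuff difference, because both differ between the two named cuffs. Only arms that fit both cuffs bear on that. On the arm-range reading, 2% to 34% of arms are within the cylindrical limit: 25 × 0.02 = 0.5 to 25 × 0.34 = 8.5 women. On the bladder reading, 58% to 96% are: 14.5 to 24 women. The conical cuff's unstated range could cut these further.

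**The case against.** The strongest reply is that no stated aim or outcome sets out to isolate shape. The trial asks how three named cuffs, as used, agree with intra-arterial pressure. If a standard cuff does badly on large arms, that is part of the question. This stands for the primary outcome and for a device-versus-device reading of the secondary comparison. It stands less well for the taper analyses, which ask about arm shape.

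Second, the Statistical Plan already has a regression of cuff-versus-cuff differences on circumferences. If both circumferences enter as separate terms, that is the same model as mid-arm circumference plus taper. This is a fair point. But the text does not say how they enter, it refers to the forearm, and its response is the difference between cuffs. The taper analyses of cuff minus intra-arterial pressure are stated on the circumference difference only.

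Third, the size of the effect rests on assumption. A large adult arm range starting at 16 cm would be odd, so the bladder reading, with its smaller shares, is at least as natural. With taper and arm size uncorrelated there is no taper bias. All of this stands.

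A reader might infer more: that one cylindrical cuff is fixed for every arm, that misfit will be reported as a shape effect, and that the design cannot tell the two apart. The documents do not support that. Cuff size is a recorded item, which would add little if it never varied. No text says a difference will be attributed to shape. Both circumferences are measured, so much of the gap can be closed in the analysis.

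**Conclusion.** The concern holds as a gap in specification. One cylindrical size is named against a bariatric conical cuff, with no selection rule and no conical range, and the taper analyses omit absolute circumference. Misfit could therefore appear as a taper slope or as a cylindrical-versus-conical difference. For the taper slope this needs two conditions that the documents neither give nor rule out: some arms outgrow the cylindrical cuff, and taper rises with arm size. The cuff-versus-cuff difference needs only the first.

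The size cannot be known from the documents. Under the assumptions shown, the spurious cuff difference runs from about 1 to 13.5 mm Hg against a 10 mm Hg criterion, and the false-positive rate for taper runs from the nominal 5% to 69%. The primary agreement of each cuff with intra-arterial systolic pressure remains valid for the cuff as used. The change is worth making because it is cheap and protects the secondary conclusions.

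**What to change.** In the Methods, say whether 16-36 cm is an arm range or bladder dimensions, give the labelled range of each cuff, and state how size is chosen.

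In the Statistical Plan:
1. Compute mid-arm circumference for each arm as the mean of the proximal and distal measurements. Include it with taper in both taper models and in the cylindrical-versus-conical regression. Correct forearm to upper arm there.
2. Use the recorded cuff size to flag whether each arm is within the labelled range of the cuff used. Report in-range arms as a sensitivity analysis.
3. Report the all-arms cylindrical-versus-conical result as *cuffs as used*, with no attribution to shape. If too few arms are in range of both cuffs, say that the trial cannot separate shape from size.

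This is a few sentences and no new measurement. The cost is precision. With taper and circumference correlated at r, the standard error of the taper slope grows by a factor of 1/√(1 − r²), before any gain from a smaller residual: 1.05 at r = 0.3, 1.15 at 0.5 and 1.40 at 0.7. The in-range subset may be small, and it would hold the smaller arms, which are the least relevant to the Background hypothesis. That is why it should be a sensitivity analysis and not the main result.

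### Six cuff readings on two arms come before an acute antihypertensive with no visible treatment-first rule: give the drug when ready, read the non-line arm first, and swap only if nothing is waiting

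*Combined protocol and SAP*

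**What the plan says.** The Methods section names three kinds of occasion for a set of readings. The first is at entry: "There will be an initial set of readings on admission". The second is during treatment: "subsequent sets of readings before a medication administration on the Vanderbilt Management Guideline for Acute Hypertension Algorithm". The third is a change of care: "A set of readings will also be attained at decision for ICU transfer or cesarean section".

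Within a set the three cuffs (large cylindrical, radial, conical) are read one after another in random order, "then repeated after swapping the cuffs over to the opposite arm". The arterial pressure is charted at the same time as each cuff reading. The swap sentence follows all three kinds of occasion and exempts none, so the natural reading is that every set has both halves. The section does not say which arm carries the radial line.

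On urgency, the Background states that systolic pressure above 160 mm Hg "constitutes a hypertensive crisis in a pregnant woman and requires urgent treatment to minimize risk for cerebral hemorrhage", and later that "SBPs this high place the preeclamptic parturient at serious risk for hemorrhagic stroke". Systolic pressure above 160 mm Hg is also an inclusion criterion. The local acute-hypertension guideline is cited as reference 20, but its content is not reproduced.

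**The concern.** Followed as written, the protocol has staff complete six sequential inflations and an arm swap before an antihypertensive is given, in women whom it describes as at risk of stroke. A drug may equally be due at the admission set or at an ICU or cesarean decision. No visible text gives treatment priority, caps the time for a set, permits a shorter one, or says which readings to drop.

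There is also a data-quality side. The reference is a radial line. A cuff inflated on the same arm interrupts flow to that catheter, so a truly simultaneous cuff-arterial pair is expected only from the other arm. If a set has to be cut short, the half to protect is therefore the non-line arm, and the current wording does not put it first.

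**Working it through.** **Count of readings.** 3 cuffs × 2 arms = 6 per set. Without the swap, 3 × 1 = 3.

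**The plan's own figure.** The Statistical Plan states 25 patients and a 10 mm Hg clinically significant difference. The Background's 2012 obstetric report gives an SD of 17 mm Hg for the oscillometric-minus-arterial systolic difference. Assuming two-sided alpha 0.05 and 80% power (the plan states neither), a one-sample t calculation gives 24.67, so 25, with 80.6% power at n = 25. Other assumptions come close too (SD 15 with 90% power gives 24 to 26), so the match is not unique. It does show that 25 can be reached with one difference per patient, without the second-arm repeat.

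**Inputs for the precision cost.** n = 25 and SD 17 for a single difference come from the documents. The following are assumed: within-patient correlation (ICC) 0.3 to 0.9; equal correlation among all readings of a patient; an admission set plus k = 1 to 4 medication sets; and valid pairs from both arms under the current plan. Let m be the number of readings per cuff per patient. The current plan gives m = 2(1 + k). With admission two-arm and medication sets one-arm, m = 2 + k. With the non-line arm only, m = 1 + k.

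**Mean bias.** Half-width = t × 17 × √[(ICC + (1 − ICC)/m)/25], with t = 2.064 on 24 degrees of freedom.
- m = 2, ICC 0.3: 2.064 × 17 × √(0.65/25) = 5.66.
- m = 1: 2.064 × 17/5 = 7.02.

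**Each limit of agreement.** Half-width = 1.96 × √[Var(mean) + 1.96² × Var(SD)], with SD² estimated as MSB/m + (1 − 1/m) × MSW from a one-way analysis of variance by patient.
- m = 1: Var(mean) = 289/25 = 11.56 and Var(SD) = 289/48 = 6.02, so 1.96 × √(11.56 + 3.84 × 6.02) = 11.54.
- m = 2, ICC 0.3: Var(mean) = 7.51 and Var(SD) = 3.25, so 1.96 × √(7.51 + 3.84 × 3.25) = 8.77.

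The table shows ICC 0.3, the end of the assumed range where the loss is largest (half-widths in mm Hg).

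| Case | m now → then | Mean bias | Each limit |
|---|---|---|---|
| Admission two-arm, 2 medication sets, both arms used | 6 → 4 | 4.53 → 4.84 (+0.31) | 6.30 → 7.00 (about +0.7) |
| Admission and 1 medication set, non-line arm only | 4 → 2 | 4.84 → 5.66 (+0.82) | 7.00 → 8.77 (+1.77) |
| One set per patient, non-line arm only | 2 → 1 | 5.66 → 7.02 (+1.36) | 8.77 → 11.54 (about +2.8) |

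The first row is the largest mean-bias increase over k = 1 to 4 when admission stays two-arm. The smallest, at ICC 0.9 and k = 4, is 6.69 → 6.72. If the primary analysis uses non-line-arm pairs only, the second and third rows apply, even where swaps were done. If line-arm pairs are unusable anyway, the valid count is 1 + k under either plan and nothing is lost.

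**Weighting.** Suppose untreated sets keep six readings, treated sets have three, and all pairs are pooled. With one set of each kind, the treated share falls from 6/12 = 50% to 3/9 = 33%. With two treated sets and one untreated, it falls from 12/18 = 67% to 6/12 = 50%. The Background reports that "outside the normal ranges NIBP tended to under read at higher pressures", so unweighted pooling would tilt the estimated bias toward milder episodes, and line-arm pairs would come only from those episodes.

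**The case against.** The strongest reply is that treatment is governed by the algorithm, which is not in the documents and may already fix timing. The Background also ties therapy to persistent severe hypertension, so a confirmation interval may exist in which readings cost nothing. These women have an arterial line, so nothing shows that a treatment decision waits on a cuff. All of this stands as a limit on the harm that can be claimed. It does not supply the missing sentence on how study readings yield to the drug.

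A second reply is that the swap has uses. It balances cuff against arm and gives each cuff a second arm geometry for the planned circumference analyses. Because entry requires systolic pressure above 160 mm Hg, sets with no drug waiting may be few. This stands as a real cost, and the documents give no SD from which to size it.

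Third, requiring three readings while a drug waits would still put research before treatment. That is right, and it is why a stop rule is needed rather than a fixed short set.

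A reader might infer two stronger things. One is that the plan causes a known delay in minutes. The documents give no time per reading or per cuff change, so no figure can be supported. The other is that a shorter set removes severity-related selection. It does not: sets stopped for a drug will still tend to be the more urgent ones, and shortening treated sets while pooling all pairs brings in its own tilt. That staff now shorten sets ad hoc in the worst episodes is plausible, but nothing in the documents shows it.

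**Conclusion.** The concern holds in a limited form. The stated sequence puts six cuff readings on two arms before an algorithm medication, in patients whose pressure the protocol itself calls urgent, and no visible text gives treatment priority. The protocol should be changed, with the caveat that the unseen algorithm may already cover part of this.

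The precision cost is modest in most of the assumed range. The worst case is one set per patient on one arm: the mean-bias half-width of 7.02 stays below the 10 mm Hg difference, but each limit's half-width of 11.54 does not. At ICC 0.9 the limits are already that wide under the current plan (10.68 with four medication sets), and 10 mm Hg is a clinical threshold, not a stated precision target. These figures rest on SD 17 from a cohort with BMI 19 to 45, on assumed correlations and numbers of sets, and on line-arm pairs being valid. The effect on the cuff-versus-cuff comparisons and the circumference regression is unknown.

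**What to change.** In Methods:
- State that the drug is given as soon as it is ready and that study readings stop at that point, at every kind of occasion.
- In every set, take the three cuffs first, in random order, on the arm without the arterial line. Do the swap only if no treatment is waiting. Random order keeps any one cuff from being the one systematically lost when a set is stopped.
- Record the times of the readings and of the drug.

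In the Statistical Plan:
- Make non-line-arm cuff-arterial pairs the primary Bland-Altman data, with limits that allow for repeated measures within patient.
- Report line-arm pairs separately, or with arm and set in the model, so that unequal set sizes do not weight the result toward milder episodes.

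The cost is protocol wording, time fields on the record form, and fewer second-arm readings for cuff-by-arm balance and the circumference analyses. Any true difference between arms enters the primary cuff-arterial difference and can be checked only in sets where the swap was done. Reading all three cuffs on one arm also needs cuff changes on that arm. The number of patients need not change on the one-difference-per-patient calculation above.
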